Official title:

Effect of the resistance-cognitive dual-task training on frailty status and cognitive function in frail community-dwelling older adults with chronic musculoskeletal pain: A pilot randomized controlled trial

NCT number: NCT07035327

Document date: 30 July 2025

Effect of the resistance-cognitive dual-task training on frailty status and cognitive function in frail community-dwelling older adults with chronic musculoskeletal pain: A pilot randomized controlled trial

Abstract

Background: The increasing prevalence of frailty among the ageing population poses significant health challenges, including heightened vulnerability to stressors and adverse outcomes such as falls, hospitalization, and chronic musculoskeletal pain (CMP). CMP significantly contributes to functional disability. Studies indicate a strong association between pain severity and frailty, with a high prevalence of chronic pain among older adults. Cognitive decline correlates with frailty and CMP, affecting perception speed, memory, and verbal fluency.

While physical activity is effective in improving physical functions and reducing pain, hence it may improve physical frailty, its impact on cognitive improvement is limited. Current research lacks comprehensive interventions targeting cognitive frailty. Dual-task training (DTT), which integrates motor and cognitive tasks, has shown promise in enhancing physical and cognitive functions in populations with neurological conditions and cognitive impairments. This study explores the potential of DTT to improve cognitive functions and frailty status in frail individuals with CMP.

Methods: This is a pilot randomized controlled trial of around 38 community-dwelling older adults with chronic musculoskeletal pain and frailty. They will be randomly assigned to either the intervention (n=19) or control group (n=19). The intervention group will receive resistance training and cognitive tasks simultaneously, while the control group will perform resistance exercises only. Both groups will perform exercises (twice/week) under supervision for 10 weeks.

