The entire program will be scheduled to span 10 weeks, with exercise sessions occurring twice per week on non-consecutive days. The exercise frequency will be established based on the American College of Sports Medicine's guidelines (Liguori et al. 2022), in which resistance exercise is recommended for at least two days per week.

- (i) Intervention group

Participants in the intervention group will engage in a DTT training program, in which resistance training will be incorporated with cognitive tasks. Ten-minute warm-up and cool-down sessions will precede and follow each exercise session.

- Resistance training:

Participants will be instructed to perform the following exercises with proper form: (1) squat to chair, (2) seated unilateral hip flexion, (3) seated unilateral knee extension, (4) standing unilateral knee flexion and (5) bilateral calf raise. The lower limb exercises will be followed by four upper limb exercises: (6) seated elbow flexion, (7) twisting a towel, (8) seated horizontal opening of arms and elbow, (9) seated diagonal opening of arm and elbow. The procedures of these exercises are described in Appendix 3. The modified BorgCR-10 scale will be adopted to determine the intensity of exercise (Borg, 1998). During the initial two-week familiarization period, one set of 10-15 repetitions at an intensity of 4-5 will be performed. From the third to the twelfth week, participants will perform two sets of 8-12 repetitions at an intensity of 5-6 for each exercise (Liguori et al., 2022). A two-minute rest period will be allowed between sets. Participants will be instructed to execute the concentric and eccentric phases over approximately 2.5 seconds to enhance muscle strength and power. Loads will be adjusted using ankle and wrist weights for exercises (1) to (6), and elastic bands with different resistance for exercises (8) and (9). A standard towel will be used for exercise (7), and subjects will be asked to twist and squeeze the towel with maximal force for 10 repetitions if the pain level is not increased (Izquierdo et al., 2017; Coelho-Júnior & Uchida, 2021).

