task without making mistakes in one session. A three-digit odd number will be randomly generated by the computer as a starting number to ensure participants will not rely on the memorized sequence but actively process each number.

There will be no specific combination of cognitive tasks and resistance exercises, it will be selected randomly upon each resistance exercise. However, each participant should perform each cognitive task for a similar number of times in one session.

(ii) Control group:

Subjects in the control group will perform the resistance exercises only without receiving any cognitive training. Ten-minute warm-up and cool-down sessions will precede and follow each exercise session. Subjects will be instructed to maintain their usual physical activity level throughout the program.

Inclusion and exclusion criteria

Adults, of either sex, aged 60 years or above, living in Hong Kong, being able to read and communicate verbally, screened frail using the Tilburg Frailty Indicator (TFI) (total score ≥ 5) with report of memory problems (question 9) (Gobbens et al., 2010), experiencing any CMP with a pain level higher or equal to 4 in the numerical pain rating scale over a consecutive 3-month period will be recruited.

Any individuals with either of the following will be excluded: absence of frailty; surgical procedure in the lower limbs or the vertebral column; wheelchair bound or inability to walk for five minutes; severe balance impairment; uncompensated cardiac or vascular condition; acute inflammatory musculoskeletal conditions; ongoing cancer; dementia; neurological diseases such as stroke, Parkinson's disease, cerebellar disease, myelopathy, and peripheral neuropathy; mental illnesses such as schizophrenia, bipolar, psychosis, borderline personality disorder; illiteracy.

Sample size consideration

As this is a pilot study, the study has been designed to generate data that will be used for setting up future larger randomised controlled trials. The sample size has been selected to evaluate the feasibility, safety and preliminary efficacy of the intervention. An exploratory sample size of 30 participants will be recruited in this study, in which 15 of them will be randomly allocated to the intervention group performing DTT, and the control group. To anticipate a 20% loss, the sample size will increase to 38. All results from the pilot study will be helpful in sample size calculations for the future large study.

Outcome measures

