(i) Primary outcome

- Feasibility and acceptability

Feasibility will be evaluated through recruitment and compliance rates of the program. Recruitment rate will be defined as the total number of participants recruited out of the total number of participants screened. Treatment compliance will be defined as the proportion of scheduled sessions attended in each group. Acceptability will be assessed by a six-question post-program questionnaire based on the barriers to engaging in physical activity (Tiecker et al., 2024). Participants will be asked about (1) their perceived importance of physical exercise, (2) their acceptability and satisfaction of the exercises, (3) the pain or discomfort during the exercises, (4) how challenging it was to perform the exercises, (5) exercise duration, (6) whether the exercises could assist in activities of daily living. All questions will be asked to rate from a 5-point Likert scale from 'Strongly disagree' to 'Strongly agree' (Appendix 4). Participants will be asked to justify all questions to let the researchers understand their difficulties. The questionnaire will be administered at the last session of this program. For descriptive interpretation, these thresholds ($\geq 70\%$ of participants attending $\geq 70\%$ of supervised sessions and $\geq 70\%$

reporting satisfaction) will be regarded as indicative of good feasibility and acceptability.

- Frailty status:

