The health-related quality of life will be assessed by the EQ-5D-5L questionnaire. It has a validated Hong Kong Chinese version (Wong et al., 2019). The questionnaire consists of 5 dimensions of health, including mobility, self-care, usual activities, pain/discomfort and anxiety/depression. Each dimension will be rated from 1 (no problem) to 5 (extreme problems). It also has an EQ-VAS scale to self-rate the overall health perception from 0 (worst health) to 100 (best health). The questionnaire will be administered before and after the intervention programme.

Sociodemographic data will also be collected, including age, gender, body mass index, marital status, living status, mobility status, educational level, employment status, lifestyle variables (exercise habit, smoking, alcohol intake), number of self-reported comorbidities, and any presence of polypharmacy (i.e. concurrent use of ≥ 5 drugs) in the baseline assessment.

Statistical analysis

Descriptive statistics with means (SDs) or medians (IQRs) for continuous variables, and counts (percentages) for categorical variables will be reported for the demographics of the participants. Shapiro-Wilk test will be used to check data for normality. The recruitment, compliance and acceptability rates will be presented as percentages with 95% confidence intervals (95% CIs) to describe the feasibility and acceptability of the program. For the first and second objectives, independent t-tests for parametric statistics or Mann-Whitney U Test for non-parametric statistics will be used to compare baseline statistics between the intervention and control groups. Mixed ANOVA will be used to show the differences of change in outcome measures between both groups, and post-hoc tests will be used to check for differences in the outcomes between pre- and post-intervention in both groups. Statistical analyses will be performed using SPSS software version 29 (IBM, New York, USA). The level of significance will be set at $p < 0.05$.

Ethical considerations

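### Compliance is defined on sessions and given a 95% CI with no stated unit of analysis; a plain percentage interval on pooled sessions would be too narrow

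*Combined protocol and SAP*

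**What the plan says.** All references are to the combined protocol and SAP.

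- **Outcome measures, (i) Primary outcome, Feasibility and acceptability.** "Feasibility will be evaluated through recruitment and compliance rates of the program". The definition follows: "Treatment compliance will be defined as the proportion of scheduled sessions attended in each group". The same paragraph sets a descriptive benchmark that counts people: at least 70% of participants should attend at least 70% of the supervised sessions.
- **Statistical analysis.** "The recruitment, compliance and acceptability rates will be presented as percentages with 95% confidence intervals (95% CIs"). Nothing is said about how the interval is calculated, what the denominator is, or whether several sessions from one person are allowed for.
- **Treatment.** "The entire program will be scheduled to span 10 weeks, with exercise sessions occurring twice per week on non-consecutive days". The resistance-training paragraph of the same section says: "From the third to the twelfth week, participants will perform two sets of 8-12 repetitions".
- **Abstract, Methods.** "They will be randomly assigned to either the intervention (n=19) or control group (n=19").
- **Sample size consideration.** "An exploratory sample size of 30 participants will be recruited in this study", and then "To anticipate a 20% loss, the sample size will increase to 38".

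**The concern.** Three rates are given the same treatment in the Statistical analysis section. Recruitment and acceptability are proportions of people, so an ordinary binomial interval suits them. Compliance, as defined, is a proportion of sessions within an arm. Sessions are nested in people: a regular attender tends to attend throughout, and someone who stops misses everything afterwards. A percentage interval that takes sessions as its sample size treats a few hundred correlated observations as independent.

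The point estimate is not at risk. When everyone has the same number of scheduled sessions, the pooled percentage equals the mean of the individual percentages. What is at risk is the stated precision of a primary feasibility measure. The Sample size consideration section says the pilot exists to supply data for larger trials. An attendance rate that looks well determined but rests on 19 people per arm could mislead that planning.

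**Working it through.** **Inputs.** 19 participants per arm (Abstract). Sessions per participant m = 2 × 10 = 20 (Treatment). Scheduled sessions per arm = 19 × 20 = 380. Anticipated loss 20% (Sample size consideration). The documents give neither an intraclass correlation (ICC) nor an expected attendance rate, so both are assumptions below, shown over a range.

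**The plan's own figure.** 30 / (1 − 0.20) = 37.5, rounded up to 38, or 19 per arm. It reproduces.

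**Session-based interval.** Half-width = 1.96 × √(p(1 − p)/380). At p = 0.75: 1.96 × √(0.1875/380) = 4.4 points.

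**Effect of clustering.** Design effect = 1 + (m − 1) × ICC = 1 + 19 × ICC. The interval should be wider by its square root.

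| Assumed ICC | Design effect | Width ratio | Half-width at p = 0.75 |
|---|---|---|---|
| 0.05 | 1.95 | 1.40 | 6.1 points |
| 0.10 | 2.9 | 1.70 | 7.4 points |
| 0.20 | 4.8 | 2.19 | 9.5 points |
| 0.30 | 6.7 | 2.59 | 11.3 points |
| 0.50 | 10.5 | 3.24 | 14.1 points |

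A ratio of 2 needs ICC = (4 − 1)/19 = 0.16; a ratio of 3 needs (9 − 1)/19 = 0.42. With m = 24, as a twelfth week would imply, the corresponding values are 3/23 = 0.13 and 8/23 = 0.35.

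**What the anticipated loss would imply.** This was simulated with 20,000 runs, 19 people and 20 sessions. In the scenarios below, 20% stop at a random session, later sessions count as missed, and attendance while in the study is 80% to 95%.

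- Implied ICC: about 0.18 to 0.48.
- Width ratio: about 2.1 to 3.2.
- Coverage of the nominal 95% session-based interval: about 45% to 63%.
- Coverage of a t interval on the 19 individual percentages: about 91% to 94% at 80% attendance, and about 88% to 92% at 90% to 95% attendance.

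With 10% loss, coverage of the t interval ranged from 79% to 93%, lowest at 95% attendance with no other variation between people. With no loss and an ICC of 0.05 to 0.10, the width ratio is only 1.4 to 1.7.

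**Worked case (assumed attendance pattern).** Fifteen people attend 17 of 20 sessions; four attend the first 5 and then stop.

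1. Pooled compliance: (15 × 17 + 4 × 5)/380 = 275/380 = 72.4%.
2. Session-based interval: SE = √(0.724 × 0.276/380) = 0.0229; 95% CI 67.9% to 76.9%.
3. Participant-based interval: individual values are 0.85 (15 people) and 0.25 (4 people); SD 0.251; SE = 0.251/√19 = 0.0577; t on 18 df = 2.101; 95% CI 60.3% to 84.5%.
4. Ratio of half-widths: 12.1/4.5 = 2.7.
5. If sessions after withdrawal were dropped from the denominator, the same data would give 275/(300 + 20) = 85.9%. The denominator rule therefore moves the estimate as well as its interval.
6. On the participant-level benchmark, 15 of 19 (78.9%) reach 70% attendance, with an exact 95% CI of 54% to 94%.

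**The case against.** The strongest reply is that the plan contains no wrong calculation, because it names no calculation. The definition fits a mean of individual percentages with a participant-level interval as well as it fits a pooled binomial, since the two point estimates coincide. This stands. A reader might infer that the plan counts sessions as independent, but the text does not say so.

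A reader might also infer that the interval will be two to three times too narrow. The documents do not support that as a plain statement. It needs an assumed ICC of about 0.16 to 0.42, or the assumption that the 20% loss means stopping sessions that stay in the denominator. The plan does not say when loss occurs, whether it means stopping training or missing the final assessment, or how sessions after withdrawal are counted.

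Third, the only compliance figure with an interpretive threshold counts participants and has no session-clustering problem. The compliance rate in the Statistical analysis section might even be that proportion. The benchmark is descriptive, and no stop/go rule, test or sample-size calculation uses the interval. This limits the consequence. It does not settle the matter: the stated definition is on sessions, and nothing says which of the two quantities carries the interval.

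**Conclusion.** The concern holds in a limited form. A session-level definition combined with a percentage interval, with no unit or method stated, leads on its literal reading to error bars that are too narrow on a primary feasibility measure. The size depends on assumptions: a factor of about 1.4 to 3.2 for an ICC of 0.05 to 0.50, and about 2 to 3 if the 20% loss consists of people who stop and whose missed sessions remain counted. The participant-level 70%/70% benchmark is sound as it stands.

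This is more than a missing detail, because following the text as written could produce a misleading interval. It does not affect the compliance estimate when the full schedule is used, nor the comparison of arms on the other outcomes.

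**What to change.** Amend the feasibility paragraph under Outcome measures and the Statistical analysis section as follows.

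1. For each randomised participant, calculate the percentage of scheduled sessions attended, keeping sessions after withdrawal in the denominator.
2. Report the arm mean with a 95% CI based on participants, either bootstrap or t-based. Note that the t interval may under-cover at high attendance with dropout. The bootstrap was not checked here and, with 19 people, should not be assumed to do better.
3. For the share of participants attending at least 70% of sessions, give an exact or Wilson 95% CI with participants as the denominator.
4. State that no binomial interval will be placed on pooled sessions.

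Separately, reconcile the 10-week programme with the reference to the twelfth week in the Treatment section. At two sessions a week they imply 20 or 24 scheduled sessions per person, and every attendance percentage depends on that number.

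The cost is a sentence or two of text and no new data, since the 70% benchmark already needs attendance recorded for each person. The downside is a wider reported interval.

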Outcome measures and data analysis: Feasibility and acceptability of the programme will be assessed at the end of the training programme. Outcome measures of frailty status, cognitive function, pain level, and health-related quality of life will be assessed at the initial and the last sessions. To examine preliminary efficacy, within-group and between-group changes in pain and functional measures will be analysed.

Expected results: We expect DTT will be feasible and well-accepted, and participants receiving DTT will gain greater improvement in frailty status, physical and cognitive performances, reduction in pain, and enhancement in health-related quality of life when compared to conventional resistance training.

Keywords: Frailty, Chronic musculoskeletal pain, Exercise, Dual-task training

Introduction

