1. The 10-week resistance-cognitive DTT program is feasible and well accepted, and can improve frailty status greater in community-dwelling older adults with frailty and CMP compared to conventional resistance training.
2. Resistance-cognitive DTT program can improve cognitive function, pain levels and health-related quality of life in community-dwelling older adults with frailty and CMP to a greater extent, compared to conventional resistance training.

Research Plan and Methodology

Study design and setting

It will be a pilot randomized controlled trial on a 10-week resistance-cognitive DTT programme. 38 subjects will be recruited from the general public in Hong Kong. Potential participants will also be identified from another ongoing cross-sectional study (ChiCTR2400089069) that investigates the prevalence of frailty in community-dwelling older adults with CMP. The program will last for 10 weeks with assessments conducted at the initial and final sessions. The assessment overview and overall flow of the study can be found in Appendices 1 and 2. Subjects will receive assessments and training in the Hong Kong Polytechnic University under supervision.

Methods

Recruitment

To recruit subjects with frailty, recruitment posters will be posted on the notice boards of the Hong Kong Polytechnic University. Invitation posts and stories will also be posted on social media like Facebook and Instagram. Potential subjects will also be identified from another cross-sectional study (ChiCTR2400089069) with a similar target population. Eligibility criteria will be screened by online questionnaires. Eligible subjects will undergo face-to-face objective assessments after getting the written consent for participation. Participants will be randomized into the intervention and control groups after the initial assessment.

Randomization and allocation

Randomization and group assignment will be performed by an investigator not involved in recruitment or assessment. After participants' eligibility for enrolment is confirmed, a researcher will use a computer to automatically generate a random sequence using Excel software (Microsoft Corporation, Redmond, USA) to generate random integers, with odd numbers being the experimental group and even numbers being the control group. The grouping information will be stored in a separate folder. Participants will undergo the corresponding exercise program which will be supervised by the researcher.

Treatment

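### The mixed ANOVA is valid but ignores baseline adjustment; a baseline-adjusted ANCOVA, with within-arm and baseline comparisons kept descriptive, is a near-free improvement

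*Combined protocol and SAP*

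**What the plan says.** The Statistical analysis section gives three comparisons.

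- **Between arms over time:** "Mixed ANOVA will be used to show the differences of change in outcome measures between both groups, and post-hoc tests will be used".
- **Within each arm:** the second half of that sentence gives the purpose of the follow-up tests, a pre-post comparison made separately for the intervention and the control participants.
- **At baseline:** independent t-tests or Mann-Whitney U tests "will be used to compare baseline statistics between the intervention and control groups".

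No covariate, ANCOVA or other baseline-adjusted model is named anywhere in the document. The significance level is 0.05.

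The abstract puts the two kinds of change side by side as the means of examining preliminary efficacy: "within-group and between-group changes in pain and functional measures will be analysed".

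Appendix 1 shows TFI, FFP, SPPB, MoCA, forward digit span, CFQ, NPRS and EQ-5D-5L all measured at baseline and at the end of the intervention. Two of these are also entry criteria: a TFI total of at least 5, and "experiencing any CMP with a pain level higher or equal to 4 in the numerical pain rating scale over a consecutive 3-month period".

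On size, Sample size consideration states: "An exploratory sample size of 30 participants will be recruited in this study", that is 15 per arm, raised to 38 for 20% loss. It adds that the results will help the sample size calculation of a later large trial.

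**The concern.** The baseline scores are collected but enter the comparison only by subtraction, which fixes the baseline slope at 1. This has two costs. Precision is lost whenever the pre-post correlation is moderate. A chance baseline gap between small arms also leaks into the estimated effect, and the Randomization and allocation section states no stratification that would limit such gaps. Both matter for a pilot whose estimates are meant to plan a larger trial.

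The within-arm tests raise a problem of interpretation. Both arms do the same resistance programme, so improvement in both is plausible. In that case a significant change in one arm but not the other is a common chance pattern, yet it can be read as efficacy. For TFI and NPRS, regression to the mean after selection on a threshold may add apparent improvement in each arm.

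The baseline tests examine only whether chance produced a difference between randomised arms. They correct nothing.

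**Working it through.** **The plan's own figure.** 30/0.8 = 37.5, rounded up to 38; per arm 15/0.8 = 18.75, rounded up to 19. The stated 38 is reproduced. There is no power calculation to reproduce.

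**Inputs.** n = 15 per arm (Sample size consideration), alpha 0.05 (two-sided assumed), one pre and one post measurement. The pre-post correlation r is not given and is assumed from 0.3 to 0.95. The Outcome measures section gives test-retest reliabilities of 0.71 (CFQ) and 0.95 (NPRS), which are only proxies for a 10-week correlation. Pre and post variances are taken as equal, scores as normal.

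**1. Precision, outcomes not truncated at entry (SPPB, MoCA and CFQ, for example).**

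- Per-participant variance is 2(1 − r)SD² for the change score and (1 − r²)SD² for ANCOVA.
- The ratio is (1 + r)/2, multiplied by 1 + 1/(30 − 4) = 1.038 for estimating the slope.
- Example at r = 0.5: 0.75 × 1.038 = 0.779.
- Break-even is (1 + r)/2 = 26/27, so r is about 0.93.

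The ratio row below is rounded from formula and simulation, which agree closely. Half-widths and power are simulated (60,000 trials per setting).

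| | r = 0.3 | r = 0.5 | r = 0.71 | r = 0.95 |
|---|---|---|---|---|
| Variance ratio, ANCOVA/change score | 0.68 | 0.78 | 0.89 | 1.01 |
| 95% CI half-width (SD), change score vs ANCOVA | 0.88 vs 0.72 | 0.74 vs 0.66 | 0.56 vs 0.53 | 0.23 vs 0.24 |
| Power for 0.5 SD, change score vs ANCOVA | 20 vs 27% | 26 vs 32% | 41 vs 45% | 99 vs 99% |

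With no true effect, both methods reject in about 5% of simulated trials.

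**2. Precision, TFI and NPRS, if the screening value is the baseline.** Truncation reduces the baseline variance and so the gain. The assumed source distributions are TFI mean 5, SD 2.5, cut at 5, and NPRS mean 5, SD 2, cut at 4. The simulated ratio is about 0.95 to 1.00 for TFI (r 0.6 to 0.8) and 0.90 to 0.99 for NPRS (r 0.5 to 0.8). At r = 0.95 it is about 1.03 for both, a small loss.

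**3. Chance imbalance.**

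- P(|baseline difference| ≥ 0.5 SD) = 2[1 − Φ(0.5/√(2/15))] = 0.171 per outcome.
- The change-score contrast is shifted by (1 − r) × 0.5 = 0.35, 0.25, 0.145 and 0.025 SD at r = 0.3, 0.5, 0.71 and 0.95. ANCOVA is shifted by zero on average.
- In trials with an imbalance above 0.5 SD, the change-score test rejects a true null in about 14%, 12%, 9% and 6%. ANCOVA stays near 5%.

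**4. Within-arm tests when both arms truly improve by d SD.** With p the power of one paired t-test (noncentral t, 14 df, noncentrality d√(15/(2(1 − r)))), exactly one arm is significant with probability 2p(1 − p).

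| | d = 0.3 | d = 0.4 | d = 0.5 |
|---|---|---|---|
| r = 0.3 | 26% | 35% | 44% |
| r = 0.5 | 31% | 42% | 49% |
| r = 0.71 | 42% | 50% | 45% |

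**5. Regression to the mean alone (upper case, same assumptions as step 2).** A given arm shows a significant improvement in 15 to 28% of trials for TFI (r 0.8 to 0.6), 9 to 17% for NPRS (r 0.8 to 0.5) and 5% for NPRS at r = 0.95, against 2.5% with no regression. Both arms do so together in at most 8% (TFI) and 3% (NPRS).

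**6. Baseline tests.** Counting EQ-5D and EQ-VAS separately, there are nine baseline outcome scores. If they were independent, P(at least one p < 0.05) = 1 − 0.95⁹ = 37% under correct randomisation.

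**The case against.** The plan contains no error on this point. The group-by-time test is unbiased and holds its 5% level, and the pilot claims no power. Choosing between two valid estimators is advice. This stands, and it sets the severity.

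The gain is small at the only correlations the document hints at (11% of variance at 0.71, none at 0.95) and close to nil for TFI, one of the three frailty tools listed under the primary outcome. This also stands. The larger gains depend on r of 0.3 to 0.5.

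The conditional false-positive rates select the unlucky trials. In the rest the change-score test rejects about 3.1%, 3.6% and 4.2% at r = 0.3, 0.5 and 0.71, so the overall rate is 5%. If all 19 per arm are kept, the chance of a 0.5 SD imbalance is 12%, not 17%. Both are correct. They limit the problem to how a particular trial's estimate should be read.

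If the post-hoc tests were run only after a significant interaction, the one-arm-significant pattern would fall to about 4 to 5%. But the document states no such gate, and the abstract lists within-group change in its own right. The hypotheses are comparative throughout, so misreading is a risk, not a plan.

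The regression-to-the-mean figures rest on assumed distributions and on the screening value serving as baseline. Recruitment says "Eligibility criteria will be screened by online questionnaires" before the face-to-face assessment, while Appendix 1 places both at Day 0. The pain criterion is also a sustained one. With re-measurement the effect could vanish, and in either case it affects both arms alike and does not bias the between-arm contrast. Those figures are an upper case only.

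No decision hangs on the baseline tests. They are uninformative, not harmful.

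**Conclusion.** The concern holds as a recommendation of modest weight. The planned group-by-time test is valid, provided that term is the one reported; the words about differences of change imply it, but the plan does not name it. A baseline-adjusted estimate would be more precise by about 11 to 32% of variance for outcomes not truncated at entry, if r lies between 0.3 and 0.71. Above r of about 0.93 there is no gain, and for TFI and NPRS little or none. The largest loss found is about 1% of variance, or about 3% for truncated outcomes at r = 0.95. ANCOVA also removes, on average, the share (1 − r) of a chance baseline gap that the change score carries.

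The separate within-arm tests cannot support an efficacy statement, because ungated they disagree between arms in 26 to 50% of trials with equal true improvement of 0.3 to 0.5 SD and r of 0.3 to 0.71. All these sizes assume 15 per arm, normal scores and equal pre and post variance. The correlations are assumptions.

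**What to change.** In the Statistical analysis section:

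- For each continuous outcome, make the efficacy estimate an ANCOVA of the post-intervention score on randomised group and the baseline value of that outcome. Report it as an adjusted between-group difference with 95% CI. FFP, a 0 to 5 score that is also categorised, needs its own sentence on how it is handled.
- Report within-group change descriptively (mean change with SD or CI), and state that it carries no efficacy claim. Align the abstract with this.
- Describe baseline characteristics by arm without p-values.

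The cost is wording and one degree of freedom per model (28 to 27 at 15 per arm). Data, SPSS software and sample size stay the same. The change does not address missing end-of-programme scores, which need separate treatment.

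### The two-time-point mixed ANOVA compares only participants with a final assessment, about 30 of 38 at the planned loss; the plan provides neither call-back nor an as-randomised analysis

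*Combined protocol and SAP*

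**What the plan says.** - **Timing.** Study design and setting: "The program will last for 10 weeks with assessments conducted at the initial and final sessions". The abstract agrees: "Outcome measures of frailty status, cognitive function, pain level, and health-related quality of life will be assessed at the initial and the last sessions". Appendix 1 shows the same two columns for every efficacy outcome, so there is one post-baseline measurement.
- **Analysis.** Statistical analysis: "Mixed ANOVA will be used to show the differences of change in outcome measures between both groups". The software is given as well: "Statistical analyses will be performed using SPSS software version 29". Significance is judged at 0.05, with sidedness not stated.
- **Expected loss.** Sample size consideration: "An exploratory sample size of 30 participants will be recruited in this study", 15 per arm, and then "To anticipate a 20% loss, the sample size will increase to 38". The abstract allocates 19 to each arm.
- **Not stated.** No section defines an analysis set, a missing-data method or a sensitivity analysis, or says whether people who stop training are asked back for the final assessment. Ethical considerations says only that participants are free to withdraw.

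**The concern.** The plan answers dropout by recruiting extra people. That protects the number analysed. It does not protect the comparison between the groups as randomised, because the people who remain may differ between arms.

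Loss that differs by arm is possible here. Only the DTT arm carries verbal fluency and mental arithmetic tasks that get harder over time. If people doing poorly left that arm more often, the remaining DTT group would look better than the arm that was randomised.

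Frailty status is listed as a primary outcome and would be tested at 0.05. The pilot's results are also meant to feed the sample size of a larger trial, so an inflated difference would carry forward.

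**Working it through.** **1. The plan's own figure.** 30 / (1 − 0.20) = 37.5, rounded up to 38; per arm 15 / 0.80 = 18.75, rounded up to 19. The stated 38 is reproduced. It implies 30 analysed, or 30/38 = 78.9%, with 8 of 38 (21%) outside the comparison.

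**2. Who enters the test.** In a 2 × 2 mixed ANOVA the group-by-time F equals the squared t statistic on change scores. In a simulated data set of 38 with 8 final values missing, both came to 0.00767 on 28 degrees of freedom (30 − 2). The baseline-only participants carried no weight.

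**3. Size of bias.** The documents give no correlation, loss mechanism or loss by arm. Assumptions: no true effect, 19 per arm, 4 lost per arm, baseline-final correlation 0.6, two-sided 0.05. Bias is in outcome SDs towards DTT. Strong selection means the odds of loss are multiplied by e per SD of worse change; moderate means half that log-odds (0.5).

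| Loss pattern | Data analysed | Bias | False-positive rate |
|---|---|---|---|
| Random | 30, change score | about 0 | 5.3% |
| Strong selection, same in both arms | 30, change score | about 0 | 6.7% |
| Moderate selection, DTT only | 30, change score | 0.10 | 6.2% |
| Strong selection, DTT only | 30, change score | 0.17 | 8.7% to 8.9% |
| Strong selection, DTT only | same 30, baseline-adjusted | 0.14 | 8.2% |
| Strong selection, DTT only | all 38 assessed | about 0 | 5.1% to 5.2% |

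**4. What changing the model can do.** With two time points, the arm effect in a linear mixed model with a common baseline mean is the baseline-adjusted estimate.
- Loss that depends on baseline, in opposite directions in the two arms (correlation 0.5 to 0.7, 4 lost per arm): the change-score bias of 0.19 to 0.31 SD falls to about 0 after adjustment.
- Loss that depends on outcome in the DTT arm: 0.14 / 0.17 = 82% of the bias stays. Under a harsher pattern in which the poorest DTT responders mostly leave, bias is 0.23 to 0.31 SD unadjusted and 0.20 to 0.24 SD adjusted.

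**5. Precision.** In outcome SDs with correlation 0.6:
- Change score, 15 per arm: √(2 × (1 − 0.6) × 2/15) = 0.327.
- Change score, 19 per arm: √(0.8 × 2/19) = 0.290. The ratio is √(38/30) = 1.125.
- Baseline-adjusted, 15 per arm: √((1 − 0.36) × 2/15) = 0.292 before the cost of estimating the slope. The simulated SE is about 0.30 against 0.325, and 1 − 0.30/0.325 = 8%. The gain is thus about 8 to 10%.

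**The case against.** A reader might infer more than the documents support, in four ways.

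- **That stopping training means removal.** No section makes attendance a condition of the final assessment. Appendix 1 labels it by the end of the intervention, and compliance is measured as a proportion of sessions, so partial attenders are expected. Someone who stops but comes to the last assessment is counted. What stands is that nothing arranges for this to happen.
- **That the bias must favour DTT.** Both arms do the same resistance exercises. The Treatment section links pain flares to that exercise and provides for adapting it. Only the cognitive load is specific to one arm, and nothing in the documents says it causes dropout. Random or equally selective loss gives a bias of about 0.
- **That the larger standard error is a defect of the method.** The increase from 30 to 38 was made so that about 30 would remain. That penalty was budgeted for and disappears only if nobody is lost.
- **That a mixed model cures the problem.** It assumes data are missing at random. Where loss depends on outcome, most of the bias survives.

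It can also be said that the plan never limits itself to completers, and that a likelihood-based model might have been meant. The text does not say so, and the usual SPSS repeated-measures procedure drops cases with a missing value. Finally, this is a pilot and efficacy is called preliminary, which lowers the stakes but does not remove them.

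**Conclusion.** The point holds in this form. The stated method and schedule together compare only people with a final assessment, about 30 of 38 if loss runs at the planned 20%. The plan has no call-back and no analysis of everyone as randomised.

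The effect on the estimate is not known. Under the assumptions shown, it runs from about 0, through about 0.10 SD with moderate selection in the DTT arm only, to about 0.17 SD with strong selection there and a false-positive rate near 9% instead of 5%. These are illustrations under assumed dropout patterns, not predictions; a more extreme pattern would give more.

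This should be changed before participants start to leave, because final assessments that are missed cannot be recovered. As the trial is a pilot, it does not put the whole design in question.

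**What to change.** 1. **Main remedy.** Invite every randomised participant to the week-10 assessment whether or not they still attend training. Define the analysis set as all randomised participants in their assigned arm.
2. **Model.** Replace the mixed ANOVA with a linear mixed model with both time points as responses, a common baseline mean and an arm-by-time effect; or use baseline-adjusted ANCOVA. State that it assumes data are missing at random. Justify it by precision and by protection against baseline-dependent loss, not as a cure for outcome-dependent loss.
3. **Sensitivity and reporting.** Add an analysis that allows for data missing not at random, keep the completers' analysis as secondary, and report losses and reasons by arm.

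The cost is new wording in the Statistical analysis section, within the same software, plus a call and one assessment visit for about 8 people. Some may decline, so step 3 is needed even if step 1 is adopted.
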